This document was constructed using the Medical Research Council (MRC) Clinical Trials Unit (CTU) at University College London (UCL) (MRC CTU at UCL, henceforth the 'MRC CTU') Protocol Template Version 7.0. The MRC CTU endorses the Standard Protocol Items: Recommendations For Interventional Trials (SPIRIT) initiative. It describes the NeoCHG trial, coordinated by the MRC CTU, and provides information about procedures for entering participants into it. The protocol should not be used as an aide-memoire or guide for the treatment of other patients. Every care has been taken in drafting this protocol, but corrections or amendments may be necessary. These will be circulated to the registered investigators in the trial, but sites entering patients for the first time are advised to contact the trial team to confirm they have the most up-to-date version.

Chlorhexidine gluconate will be denoted with the abbreviation 'CHG' or as 'chlorhexidine' throughout the protocol.

COMPLIANCE

The trial will be conducted in compliance with the approved protocol, the Declaration of Helsinki 1996 (seventh revision), the principles of Good Clinical Practice (GCP) as laid down by the ICH topic E6, and applicable national regulations. For the purposes of this trial, CHG is regarded as a Clinical Trial of an Investigational Medicinal Product (CTIMP) in South Africa but not in Bangladesh.

SPONSOR

St George's, University of London is the trial Sponsor and has delegated responsibility for the overall management of the NeoCHG trial to the MRC CTU. Queries relating to sponsorship of this trial should be addressed St George's, University of London. All questions about any aspects of trial management should be directed to the trial management team at the MRC CTU.

FUNDING

MRC/NIHR/DfID/Wellcome Joint Global Health Trials Call 9 – Trial Development Grant. Medical Research Council for core support to the MRC CTU.

AUTHORISATIONS AND APPROVALS

This trial will be submitted for approval by Research Ethics Committees (REC)/Institutional Review Boards (IRB) in each of the participating countries. For oversight, the REC associated with the trial's Sponsor will review the trial protocol and relevant trial documentation.

TRIAL REGISTRATION

This trial will be registered via the ISRCTN Clinical Trial Register, where it is identified as ISRCTN69836999.

SAE REPORTING

This is a pilot study to assess the best way of applying antiseptic to low birth weight newborn babies who are in hospital. The antiseptic aims to reduce the amount of potentially harmful bacteria on the skin of newborn babies. This might be useful for preventing infections which are picked up in hospital.

This study aims to find out the best concentration of antiseptic to use, as well as how often it should be put on the babies, and whether or not it should be combined with a skin softener. In this pilot study, we will see the amount of bacteria babies have on their skin, and look carefully at whether, and how often, skin reactions occur.

The antiseptic we will test in this study is called chlorhexidine. Chlorhexidine has been widely used across the world for many decades to reduce the risk of babies dying from infection. For example, it is put on the umbilical cord of newborn babies at home in areas with high rates of deaths from infections. However, we don't know whether applying chlorhexidine to the body could reduce the risk of infection and death in newborn babies who are in hospital and have a high risk of infection because of other problems, like being premature or low birth weight.

In addition, skin softeners (also called emollients), which are often in the form of oils such as sunflower oil, have been shown in some, but not all, studies to reduce infections. We do not know whether combining emollients and an antiseptic may work even better, so we will also look at this in this pilot study.

The study will be conducted in two hospitals, one in Bangladesh, and the other in South Africa. Chlorhexidine will be put on the skin of the body of some of the babies, starting at 1-6 days of age and either on working days or on alternate working days of the week.

Different babies will get different concentrations of chlorhexidine. Some babies will also get skin softeners applied. And some babies will just be followed as normal. A computer will choose which babies get which treatment. Skin swabs will be taken from various areas of the skin of the babies, and the amount and type of bacteria on these swabs will be counted.

In addition, the skin of the babies will be closely monitored for any signs of side effects to chlorhexidine. Applying an antiseptic can make babies colder and can sometimes cause skin reactions which may make it easier for bacteria to get into the babies instead of protecting them. But we don't know how these different advantages and disadvantages balance out. This study will look at the balance between reducing numbers of bacteria and safety. In the future, we plan to test the best method to reduce the number of bacteria on newborn babies' skin we find in this study in a much larger study, to see whether it could reduce serious infections or not.

TRIAL SCHEMA

Figure 1: Trial Schema

Follow up to 28 days. Last application of CHG at day 14 after enrolment or discharge (whichever earlier)

Co-primary outcome(s)

- Change in bacterial load from baseline to final swab (efficacy)
- Adapted Neonatal Skin Condition Score (safety) (absolute score and grade)

Secondary outcomes

- Temperature (change in absolute temperature and grade (hypothermia))
- Acquisition & loss of specific bacterial species
 - Enterobacteriaceae
 - Acinetobacter
 - Staphylococcus aureus
 - Beta haemolytic streptococci (group A and B)
 - Enterococcus
 - Candida
 - Pseudomonas aeruginosa
- Serious adverse events

Note: CHG=chlorhexidine gluconate. Alternate working days are Monday, Wednesday, Friday; or Tuesday, Thursday, Saturday, depending on the standard working pattern in each country.

Figure 2: Trial Entry, Randomisation and Treatment

*E= Emollient (same timing as CHG) *NoE = No Emollient.

Note: CHG=chlorhexidine gluconate. Alternate working days are Monday, Wednesday, Friday; or Tuesday, Thursday, Saturday, depending on the standard working pattern in each country.

SUMMARY OF TRIAL

SUMMARY INFORMATION TYPE	SUMMARY DETAILS
Short title	NeoCHG
Long title	Efficacy and safety of whole-body chlorhexidine (CHG) cleansing in reducing bacterial skin colonisation of hospitalised low birth weight neonates: A pilot trial
Version	2.0
Date	29-Nov-2021
ISRCTN #	ISRCTN69836999
Study Design	Factorial randomised controlled pilot trial
Setting	Hospital neonatal units in South Africa and Bangladesh
Type of Participants to be Studied	Hospitalised low birth weight (1-2kg) babies between the ages of 1-6 days at enrolment
Ancillary Studies/Sub-studies	None
Sponsor	St George's, University of London
Interventions to be Compared	Chlorhexidine gluconate (CHG) whole body skin application in varying concentrations (2% vs 1% vs 0.5%) and varying frequency, each with or without emollient application, compared to a control group with no CHG or emollient.
Study Hypothesis	Increasing concentration and frequency of CHG skin application leads to greater reductions in bacterial colonisation. The addition of emollient improves the skin condition and safety of CHG application, permitting the more effective concentration to be used.
Primary Outcome Measure(s)	 Co-primary outcomes are: Change in bacterial load from baseline to final swab (efficacy) Adapted neonatal skin condition score (safety) (absolute score and grade)
Secondary Outcome Measure(s)	 Temperature (change in absolute temperature and grade (hypothermia)) Acquisition & loss of specific bacterial species: Enterobacteriaceae Acinetobacter Staphylococcus aureus Beta haemolytic streptococci (group A and B) Enterococcus Candida Pseudomonas aeruginosa
Randomisation	Factorial randomised controlled trial, Allocated 1:1:1:1:1:1:1:1:1:1:1:1:1 into 12 intervention arms and 1 control arm 0.5% CHG each working day with emollient

NeoCHG Protocol v2.0 29-Nov-2021

SUMMARY INFORMATION TYPE	SUMMARY DETAILS
	0.5% CHG each working day without emollient
	0.5% CHG alternate working days with emollient
	0.5% CHG alternate working days without emollient
	1% CHG each working day with emollient
	1% CHG each working day without emollient
	1% CHG alternate working days with emollient
	1% CHG alternate working days without emollient
	2% CHG each working day with emollient
	2% CHG each working day without emollient
	2% CHG alternate working days with emollient
	2% CHG alternate working days without emollient
	Control Group without emollient and without CHG
	(Alternate working days are Monday, Wednesday, Friday; or
	pattern in each country.)
Number of Participants to be	182 (babies without baseline and two post-baseline swabs on
Studied	which to assess the primary efficacy endpoint will be replaced)
Duration	12 months to complete recruitment and follow-up. Individual
	follow up during hospital admission up to day 14 after enrolment
	or discharge if earlier, and final follow up 28 days after
Funder	MRC/NIHR/DfID/Wellcome Joint Global Health Trials Call 9 – Trial Development Grant & MRC Core Funding (MRC CTU at LICL)
Chief Investigator	[name]

TRIAL ASSESSMENT SCHEDULE

TABLE 1: Trial Assessment Schedule

ASSESSMENTS						D	AYS II	N TRIA	۹L		
					Week :	1			Wee	< 2	Final follow up
Face to face visit	Screening	Random-	Day	Day	Day	Day	Day	Day	Day	Day	Day 28
Face to face or telephone	D-1 to D1	isation D1	1	2	3	4	5	8	9	10-14	
Trial participation		1									
Eligibility	Х										
Parent/carer information sheet	Х										
Informed consent	Х										
Enrolment form and		X									
randomisation ^a											
Clinical assessments											
Baseline data collection ^b	X										
Weight	Х									Х	
Temperature ^c	Х		Х	Х	Х	Х	Х	Х	Х	Xi	
Skin Score ^d	X		Х	Х	Х	Х	Х	Х	Х	Xi	
Adverse Events	Х		Х	Х	Х	Х	Х	Х	Х	X ⁱ	
Microbiology											
Nose swab ^e			х		Xe			Xe			
Cervical skin fold & umbilical swabs (pooled) ^f			х		Хţ			Xf			
Rectal swab ^g			Х		Xg			Xg			
CHG ± emollient application ^h			Х	(X)	Х	(X)	Х	(X)	Х	Xi	
Final follow up											Xj

Additional explanatory notes for investigations

Intervention & assessment days are on working days – if a day falls on a non-working day then shift next activity to the closest working day, whatever the working pattern. Alternate working days are Monday, Wednesday, Friday; or Tuesday, Thursday, Saturday, depending on the standard working pattern in each country.

^a Enrolment form completed and data entered into the database. Randomisation completed electronically.

^b Includes collecting medical history, mode of delivery, birth weight, gestational age, co-morbidities and antibiotic history. ^c Temperature to be collected once at screening. Temperature to be collected BEFORE every CHG ± emollient application and 15 minutes POST application. Skin score, temperature and AEs will be monitored daily in all groups.

^dSkin to be assessed according to the skin score in Appendix I, once at screening. Skin score to be assessed BEFORE every CHG ± emollient application and 30 minutes POST application.

^e Nose swab to be taken BEFORE any CHG ± emollient application on day 1, day 3± 1 day and day 8 ± 3 days (closest working day) and at any time on this day in the control group. See Manual of Operations (MOP) for further details on how to take swabs.

^f A pooled swab of the cervical skin and umbilicus to be taken BEFORE any CHG \pm emollient application on day 1, day 3 ± 1 day and day 8 ± 3 days (closest working day) and at any time on this day in the control group. See MOP for further details on how to take swabs.

^g Peri-rectal swab to be taken BEFORE CHG \pm emollient application on day 1, day 3 \pm 1 day and day 8 \pm 3 days (closest working day) and at any time on this day in the control group. See MOP for further details on how to take swabs. ^h CHG \pm emollient to be applied either every working day or alternative working days according to randomised allocation.

ⁱ CHG± emollient application to be continued on every working day or alternative working days according to randomised to randomisation) until day 14 or discharge, whichever is sooner.

¹ phone call if discharged. Vital status will be ascertained, together with occurrence of serious adverse events (including clinically defined sepsis, necrotising enterocolitis (NEC)) and any unscheduled visits to healthcare providers

ABBREVIATIONS

ABBREVIATION	EXPANSION
AE	Adverse event
AMR	Antimicrobial resistance
AR	Adverse reaction
CF	Consent Form
CFU	Colony forming units
СІ	Chief Investigator
СІ	Confidence interval
СНБ	Chlorhexidine gluconate
СОМ	Clinical Operations Manager
СРМ	Clinical Project Manager
CRF	Case Report Form
СТU	See MRC CTU at UCL
D	Day
DCF	Data Clarification Form
DM	Data Manager
DMC	Independent Data Monitoring Committee
DMP	Data Management Plan
DNDi	Drugs for Neglected Diseases Initiative
EU	European Union
GARDP	Global antibiotic research and development partnership
GCP	Good Clinical Practice
НАІ	Healthcare Associated Infection
ΙΜΡΑΑCΤ	International Maternal Pediatric Adolescent AIDS Clinical Trials Network
IMP	Investigational medicinal product
IRB	Institutional Review Board
ISRCTN	International Standard Randomised Controlled Trial Number

ABBREVIATION	Expansion	
ІТТ	Intention-to-treat	
LMIC	Low or middle income country	
MedDRA	Medical Dictionary for Regulatory Activities	
MHRA	Medicines and Healthcare products Regulatory Agency	
МОР	Manual of Operations	
MRC	Medical Research Council	
MRC CTU at UCL	Medical Research Council Clinical Trials Unit at University College London (also generally abbreviated to "CTU")	
NEC	Necrotising enterocolitis	
NeoAMR	Neonatal antimicrobial resistance (programme)	
NIMP	Non-investigational-medicinal product	
PENTA	Paediatric European Network for Treatment of AIDS	
Ы	Principal Investigator	
PIS	Patient Information Sheet	
QMAG	Quality Management Advisory Group	
RCT	Randomised controlled trial	
REC	Research Ethics Committee	
RGC	Research Governance Committee	
SAE	Serious adverse event	
SAP	Statistical Analysis Plan	
SAR	Serious adverse reaction	
SD	Standard deviation	
SGUL	St George's University of London	
SOP	Standard operating procedure	
SmPC	Summary of Product Characteristics	
SSA	Site-specific approval	
SUSAR	Suspected unexpected serious adverse reaction	
TMF	Trial Master File	

ABBREVIATION	Expansion
TMG	Trial Management Group
TSC	Trial Steering Committee
UAR	Unexpected adverse reaction
WHO	World Health Organization

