1.4.7 RATIONALE FOR DESIGN OF NEOCHG

Given that several questions remain about the safest regimen of chlorhexidine in low birth weight newborn babies, as well as the effect of emollient, a design which permits several questions to be answered simultaneously is preferred. The factorial design enables multiple interventions to be tested more efficiently than comparing each intervention separately. Including a control group enables the effect of chlorhexidine to be compared to the current standard of care.

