3.3 NUMBER OF PATIENTS

182 babies will be randomised in total. Babies without a baseline and two post-baseline swabs will be replaced to maintain power. All baseline and post-baseline results will be included in the analysis.

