9.3 SAMPLE SIZE

The trial is designed as a permuted block factorial, with an additional control per permuted block. 182 neonates in 14 permuted blocks provides 90% power to detect a difference of 0.66 standard deviations (SDs) between concentrations and 0.47 SDs between the different levels of frequency and emollient (two-sided α =0.05) (80% power for 0.58 and 0.41 SDs, respectively). This also provides 90% power to detect a difference of 1.04 SD between each concentration and control, and 0.96 SD between each level of frequency/emollient and control (0.92 and 0.96 SDs at 80% power). Previous studies have found varying effects of chlorhexidine on log colony counts: a decrease from baseline to 24h of 0.2SD with 1% chlorhexidine in Nepal and 2SDs with 2% chlorhexidine in the USA.^{18,21}

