The effect of each treatment arm will be assessed within a single model with each factor being fitted independently as a factor, and not as a continuous variable. Comparison of main effects within arms will be assessed using the estimate and 95% confidence interval of the comparison of differences between factors and in comparison, to control. As this is a pilot trial, the sample size was not powered to robustly detect interactions between chlorhexidine concentrations/frequencies and emollients and so we will not test these formally, but will use exploratory analyses to assess whether there is any evidence supporting individual interactions testing each one, one at a time. As this is a pilot trial and the two co-primary outcomes capture different aspects (efficacy and safety) there will be no adjustment for multiple testing, nor for the two different bacterial load outcomes since we expect a reduction in colonisation on the skin, but potentially no change in colonisation peri-rectally.

Similar mixed models will be used to analyse change in skin temperature after vs before each application, including individual as a random effect, the change in temperature as the outcome and the pre-application (baseline) temperature as a factor. Acquisition and loss of each species will be analysed as a binary outcome variable, compared with baseline, in the relevant population (those without the species of interest at baseline, or with the species of interest at baseline, respectively).

Presence/absence of each species at each assessment will also be compared between randomised groups using mixed models, again with individual as a random effect, and with baseline presence as a factor.

Frequency of SAEs will be tabulated by randomised group, and compared using exact logistic models (or time-to-event models if AEs occur in >10% of the trial population overall). SAEs will also be tabulated by grade. Similar analyses will be conducted for the AEs in Appendix II.

A Statistical Analysis Plan will be written and approved by the Trial Management Group (TMG) and the DMC before the first interim analysis is reviewed by the DMC.

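### A second control per block would sharpen the planned comparisons with control by about a fifth within the same 182 babies, at a small cost to the factor contrasts

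*Protocol*

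**What the plan says.** The Randomisation row of the Summary of Trial sets "Allocated 1:1:1:1:1:1:1:1:1:1:1:1:1 into 12 intervention arms and 1 control arm". Section 3.3 states that "182 babies will be randomised in total". Section 9.3 describes the blocks: "The trial is designed as a permuted block factorial, with an additional control per permuted block".

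Section 9.3 then gives detectable differences for two families of contrast. Within chlorhexidine: "182 neonates in 14 permuted blocks provides 90% power to detect a difference of 0.66 standard deviations (SDs) between concentrations", with 0.47 SD for frequency and for emollient. Against control: "This also provides 90% power to detect a difference of 1.04 SD between each concentration and control", and 0.96 SD for a frequency or emollient level. The 80%-power figures are 0.58 and 0.41 SD within chlorhexidine, and 0.92 and 0.96 SD against control.

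Section 9.5 fits the three factors in one model and reports "the estimate and 95% confidence interval of the comparison of differences between factors and in comparison, to control". On the purpose of the control arm, Section 1.4.7 says: "Including a control group enables the effect of chlorhexidine to be compared to the current standard of care". Section 1.4.6 gives the trial's specific aim as choosing the regimen for a later, larger trial.

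**The concern.** Equal allocation suits a comparison of 13 separate arms, but Section 9.5 compares pooled factor levels. Each concentration pools four arms and each frequency or emollient level pools six, while control pools nothing. The comparisons with control are therefore made at 4:1 and 6:1, and most of their variance comes from the 14 controls. The protocol gives no reason for one control per block.

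What is at stake is the precision of the comparison that the control arm exists to provide, for bacterial load and also for skin score, temperature and SAEs. As an illustration for safety, no events in 14 controls leaves an exact two-sided 95% upper limit of 23% (1 − 0.025^(1/14)). No events in 26 leaves 13%.

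**Working it through.** **Inputs.** 182 babies, 14 blocks, 12 regimens plus 1 control per block, two-sided α = 0.05 (Summary of Trial; Sections 3.3 and 9.3). Babies without the required swabs are replaced, so no dropout allowance is made. I assume one summary value per baby with SD 1, independent between babies.

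**Group sizes now.** 14 × 13 = 182, so N reproduces. Control 14; concentration 4 × 14 = 56; frequency or emollient level 6 × 14 = 84.

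**Formulas.** SE = √(1/n₁ + 1/n₂). Detectable difference = (1.960 + 1.282) × SE = 3.2415 × SE at 90% power, and 2.8016 × SE at 80%.

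**The plan's own figures.** From 14 blocks:

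| Contrast | SE | 90%: computed (stated) | 80%: computed (stated) |
|---|---|---|---|
| Concentrations, 56 v 56 | 0.189 | 0.61 (0.66) | 0.53 (0.58) |
| Frequency or emollient, 84 v 84 | 0.154 | 0.50 (0.47) | 0.43 (0.41) |
| Concentration v control, 56 v 14 | 0.299 | 0.97 (1.04) | 0.84 (0.92) |
| Level v control, 84 v 14 | 0.289 | 0.94 (0.96) | 0.81 (0.96) |

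Most of the stated figures do not follow from these sizes. Power at 0.66 SD is 93.7%, at 0.47 SD 86.1%, and at 0.41 SD 75.7%. A t reference, a one-sided test, Bonferroni corrections and a 2-df F test were tried, and none reproduces the whole set. The level-v-control figure of 0.96 SD cannot hold at both 80% and 90% power. It has 91.4%.

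**Share of variance from control.** (1/14)/(1/14 + 1/56) = 80% for a concentration; (1/14)/(1/14 + 1/84) = 86% for a level.

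**Two controls per block.** Block size 14, and 182/14 = 13 complete blocks. Control 26; concentration 52; level 78.

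| Contrast | SE, now → two controls | Change | 90%-power difference | 80%-power difference |
|---|---|---|---|---|
| Concentration v control | 0.299 → 0.240 | −19.6% | 0.97 → 0.78 | 0.84 → 0.67 |
| Level v control | 0.289 → 0.226 | −21.6% | 0.94 → 0.73 | 0.81 → 0.63 |
| Concentrations | 0.189 → 0.196 | +3.8% | 0.61 → 0.64 | 0.53 → 0.55 |
| Frequency or emollient | 0.154 → 0.160 | +3.8% | 0.50 → 0.52 | 0.43 → 0.45 |

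At 0.66 SD, the protocol's own concentration difference, power against control rises from 59.8% to 78.5% (concentration) and from 62.8% to 83.0% (level). Within chlorhexidine, power falls from 93.7% to 92.0% at 0.66 SD, from 86.1% to 83.5% at 0.47 SD, and from 75.7% to 72.6% at 0.41 SD.

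**Counting control only once.** Sum the variances of the three concentration contrasts, the frequency contrast, the emollient contrast and one overall chlorhexidine-v-control contrast:

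- Now: 3(2/56) + 2(2/84) + (1/14 + 1/168) = 0.155 + 0.077 = 0.232.
- Two controls: 3(2/52) + 2(2/78) + (1/26 + 1/156) = 0.167 + 0.045 = 0.212.
- Three controls per block: 0.213, and 182 does not divide into blocks of 15.

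The two designs tie when the overall control contrast carries weight (0.1667 − 0.1548)/(0.0774 − 0.0449) ≈ 0.37 relative to one factor contrast. Above that weight, two controls per block gives the lower total.

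**The case against.** The strongest reply is that one control per block is a deliberate and disclosed choice that fits the aim. Section 1.4.6 seeks a regimen, and the Study Hypothesis concerns concentration, frequency and added emollient, all of which are comparisons within chlorhexidine. Section 9.3 openly shows that control comparisons are weaker, and its figures are somewhat more pessimistic than mine. Two controls per block takes precision from the contrasts that matter most. For frequency and emollient it widens an existing shortfall against the stated 90% at 0.47 SD. It also lowers the number of babies on chlorhexidine from 168 to 156, and each regimen from 14 to 13, in a trial where regimen safety is a co-primary concern. Thirteen blocks do not split evenly between two sites, though the protocol sets no per-site target.

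Much of this stands. It rules out two stronger readings that a reader might infer:

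- **That the allocation is an error or contradicts the analysis.** It does neither. Section 9.3 specifies the extra control per block and powers the resulting contrasts.
- **That seven separate results are undermined** (three concentrations, two frequencies and two emollient levels against control). These are overlapping regroupings of the same treated babies against one control group. Counted once, the total variance falls by about 9% (0.232 to 0.212), not by the size of the gain on the control contrasts alone.

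The gain in power also depends on the true effect. Section 9.3 cites earlier decreases from baseline of 0.2 and 2 SD. If those were differences from control, power for a concentration would be about 10% now and 13% with two controls at 0.2 SD, and essentially 100% either way at 2 SD. The benefit lies in the range between.

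The objection does not remove the point. The control comparisons are planned and powered, the loss on the factor contrasts is small, and the trade is favourable unless the control contrast is given less than about 0.37 of the weight of one factor contrast.

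**Conclusion.** This is a cheap improvement to consider, not a fault in the plan. The imprecision against control is avoidable at small cost; the documents do not support calling it needless, because avoiding it takes something from the contrasts that serve the main aim.

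The standard error of the control contrasts would fall by about 20% to 22%, and that of the factor contrasts would rise by 3.8%. These percentages do not depend on the SD, and they are unchanged by any gain from baseline adjustment or repeated swabs that acts equally in all groups. The detectable differences in SD units do rest on a common SD, independent babies and one value per baby. The protocol does not say whether recruitment had begun at version 2.0; if it had, only later blocks could change and the gain would be smaller.

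Apart from the allocation, Section 9.3 needs correcting, because most of its detectable differences do not follow from 14 blocks.

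**What to change.** Change the allocation in the Summary of Trial and in Section 9.3 to 12 regimens plus two controls per block, 13 blocks, 182 babies. If recruitment has begun, apply it only to blocks not yet allocated and state the resulting group sizes. If the sponsor prefers one control per block, a sentence in Section 1.4.7 or 9.3 giving the reason would settle the matter.

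Under either choice, restate the detectable differences in Section 9.3 from the actual group sizes. Correct the frequency and emollient figures, and the 0.96 SD against control that stands at both power levels.

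Cost: a new randomisation list and protocol wording, with no extra babies. In return for the gain against control, the factor contrasts lose 3.8% in standard error, power for frequency and emollient at 0.47 SD falls from about 86% to about 83%, and 12 fewer babies receive chlorhexidine.

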4.2 RANDOMISATION CODES & UNBLINDING

The allocation will not be blinded as this is not practical given the number of factors evaluated. However, the efficacy co-primary endpoint (bacterial colonisation) will be assessed by laboratory staff blinded to randomisation.

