5 TREATMENT OF PATIENTS

5.1 INTRODUCTION

All babies will receive routine care as per normal procedures in each site, except for the interventions of the trial including chlorhexidine skin wipes and emollient, and the trial's clinical and microbiological assessments.

- Control group without CHG and without emollient
- 0.5% CHG each working day with emollient
- 0.5% CHG each working day without emollient
- 0.5% CHG alternate working days with emollient
- 0.5% CHG alternate working days without emollient
- 1% CHG each working day with emollient
- 1% CHG each working day without emollient
- 1% CHG alternate working days with emollient
- 1% CHG alternate working days without emollient
- 2% CHG each working day with emollient
- 2% CHG each working day without emollient
- 2% CHG alternate working days with emollient
- 2% CHG alternate working days without emollient

Alternate working days are Monday, Wednesday, Friday; or Tuesday, Thursday, Saturday, depending on the standard working pattern in each country. The treating clinician(s) and parents/carers will be unblinded to the allocated treatment. Chlorhexidine will be diluted locally, in the central pharmacy, following the site-specific pharmacy SOPs/guidelines.

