5.2 TRIAL TREATMENTS

All babies participating in the trial, except those randomised to the control group, will receive chlorhexidine with or without emollient. Treatment should start immediately following randomisation as described below, following the randomised frequency schedule.

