9.2 OUTCOME MEASURES

9.2.1 CO-PRIMARY OUTCOME MEASURES

- Skin bacterial load change in colony forming units (CFUs) in the nose (1 swab), cervical skin folds and umbilicus (1 pooled swab), and peri-rectal area (1 swab) from randomisation (before chlorhexidine application) to D3+/- 1 day and D8 +/- 3 days microbiology data collection (efficacy).
- Modified neonatal skin condition score (see Appendix I) used before each application of chlorhexidine, or alternate working days in controls (safety). The primary analysis of this outcome will consider the absolute score. Secondary analysis of this outcome will consider graded toxicity (see Appendix I).

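### The schedule ties the baseline swabs to the first application and not to randomisation, so in this open-label trial the baseline of the efficacy co-primary can depend on known allocation

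*Protocol*

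**What the plan says.** In Table 1 (Trial Assessment Schedule), baseline data, weight, temperature and skin score are marked in the Screening column. The three swab rows have no mark there. Their first mark is under Day 1, to the right of the column headed Randomisation D1.

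Notes e, f and g give the timing. Note e reads "Nose swab to be taken BEFORE any CHG ± emollient application on day 1", and all three notes then add, for the same swab days, "and at any time on this day in the control group". Section 5.2 says of the treated arms: "Treatment should start immediately following randomisation as described below".

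Section 9.2.1 measures the efficacy co-primary "from randomisation (before chlorhexidine application) to D3+/- 1 day" and to day 8, and Section 6.2 does the same. Section 9.5 compares within-baby differences over time and adjusts for the baseline value of each outcome.

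On blinding, Section 4.2 says "The allocation will not be blinded as this is not practical given the number of factors evaluated" and Section 5.1 says "The treating clinician(s) and parents/carers will be unblinded to the allocated treatment". The stated protection is that bacterial colonisation "will be assessed by laboratory staff blinded to randomisation".

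No inclusion or exclusion criterion requires a baseline swab. Section 3.3 provides for the case where one is lacking: "Babies without a baseline and two post-baseline swabs will be replaced to maintain power". The same section keeps all available results in the analysis.

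**The concern.** A baseline should be fixed before anyone at the bedside knows the arm. Here the swab's only stated limit is the first application. In a treated baby swabbed after randomisation, the swab falls in the interval between allocation and a first application meant to follow directly. In a control it may be taken at any hour of the day. The effort made, the technique, and whether a swab is taken at all are open to the same influence.

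This baseline is used twice: as the starting point of the change and as the adjustment covariate. A systematic difference between arms in how it is obtained carries into the treatment estimate. A blinded laboratory protects the counting of colonies but not the sampling.

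There is a second, smaller consequence. Because no swab is required before the allocation is released, a baby can be randomised with none taken. Part of the replacement rule then depends on an avoidable event after open allocation.

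**Working it through.** **Order of events, from the protocol.**

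1. Baseline data, weight, temperature, skin score: Screening column, before randomisation.
2. Randomisation: its own column, Day 1.
3. Nose, pooled and peri-rectal swabs: first marked under Day 1, next column along, limited only by the first application.
4. First application: Day 1, directly after randomisation.

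Section 3.5 says that consenting families have a baseline assessment and are then randomised, but does not name swabs. Section 4 refers enrolment assessments back to the schedule, which does not place swabs at screening. No section requires a swab before allocation.

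**Group sizes.** Section 9.3 gives 182 babies in 14 permuted blocks, and 182 / 14 = 13 per block, one for each of the 12 intervention arms plus one control. That gives 14 controls, 4 × 14 = 56 babies per concentration and 6 × 14 = 84 per level of frequency or emollient.

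**Effect of a differential baseline.** Suppose the control baseline is shifted by b SD because of how it was taken, with no true difference. Let ρ be the correlation between baseline and follow-up.

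- Unadjusted change score: spurious difference = b.
- Baseline-adjusted estimate (the planned primary model): spurious difference = ρ × b.

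The protocol gives neither b nor ρ. With b = 0.2 and ρ from 0.3 to 0.7, both assumed:

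- change score: 0.2 SD;
- adjusted: 0.3 × 0.2 = 0.06 SD to 0.7 × 0.2 = 0.14 SD.

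**Effect on the error rate, 14 controls against 56 in one concentration.** As a simplification I use one post-baseline swab and a normal approximation. The factor for group sizes is √(1/14 + 1/56) = 0.299. The SD is √(2(1 − ρ)) for a change score and √(1 − ρ²) after adjustment. The nominal two-sided level is 0.05.

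| ρ | Change score: SE, shift/SE, error | Adjusted: SE, shift/SE, error |
|---|---|---|
| 0.3 | 0.354, 0.57, 0.087 | 0.285, 0.21, 0.055 |
| 0.5 | 0.299, 0.67, 0.103 | 0.259, 0.39, 0.067 |
| 0.7 | 0.231, 0.86, 0.139 | 0.213, 0.66, 0.101 |

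With b = 0.1 the adjusted error is 0.051 to 0.062, and with b = 0.3 it is 0.061 to 0.166. The adjusted column is the relevant one for the planned model.

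**Scale.** Section 9.3 states 1.04 SD as detectable with 90% power between a concentration and control. The adjusted shift of 0.06 to 0.14 SD is about 6% to 13% of that (0.06 / 1.04 and 0.14 / 1.04).

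**Which contrasts are exposed.** All 12 intervention arms share one timing rule, before the first application. The written split in timing is between treated babies and controls only.

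**The case against.** The best case for the protocol has five parts.

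- **No sentence says that the swabs follow randomisation.** Both fall on the same trial day, and Section 3.5 puts a baseline assessment before randomisation. The wording in 9.2.1 also fits a swab taken just before allocation. This stands: the order is inferred from the columns and the notes. It does not remove the point, because nothing rules the later order out and the schedule as laid out leads to it.
- **The clause for controls has an innocent reading.** Each note covers three swab days in one sentence, and controls have no application to be swabbed before. A reader might infer that the clause proves the arm is known when the Day 1 swab is taken. It does not, since a swab taken before randomisation satisfies it in every arm.
- **The bedside exposure is partly inferred.** The protocol does not say who takes the swabs, and it leaves technique to a Manual of Operations that is not at hand. That the swab-taker knows the arm is likely, not stated.
- **The likely effect is modest.** Colonies are counted blind, the primary model adjusts for baseline, and the assumed example is small beside 1.04 SD. This stands as a limit on size. Adjustment shrinks a differential shift but does not remove it.
- **Replacement adds babies and removes no results.** A reader might infer that babies without a baseline swab are dropped. Sections 3.3 and 9.5 keep all available results, so the harm from replacement is limited.

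**Conclusion.** The point holds as a weakness of the schedule. The baseline of an efficacy co-primary is tied to the first application in an open-label trial, and no rule requires it before the arm is known. Baseline timing, technique or completeness can therefore differ by arm, and a baby can be randomised with no baseline swab taken. The comparisons with the 14 controls are the most exposed.

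The size is unknown. The 0.06 to 0.14 SD, and the error of 0.055 to 0.101 against 0.05, rest on an assumed shift of 0.2 SD, an assumed correlation of 0.3 to 0.7 and a single follow-up swab. The direction cannot be told from the protocol.

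Two stronger readings are not supported. One is that the efficacy comparisons are biased: the documents show an opportunity for bias and no differential. The other is that contrasts between concentrations, frequencies or emollient levels are equally affected: all treated babies follow the same timing rule, so only a difference in technique or completeness between treated arms could reach those contrasts.

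The order of sampling is set by the protocol's schedule, and an analysis plan could not repair it afterwards. That makes a small correction worthwhile even though the likely effect is modest.

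**What to change.** - In Table 1, schedule the three baseline swabs after consent and eligibility and before the allocation is released, on the day of randomisation.
- Add a confirmation to the randomisation worksheet that all three were taken. Section 4.1 already has the system check eligibility automatically, so the confirmation can be checked at the same step.
- In notes e to g, limit the clause "and at any time on this day in the control group" to the day 3 and day 8 swabs.
- In Sections 6.2 and 9.2.1, define baseline as the swab taken before randomisation.

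The cost is a reordering of steps within one day, one extra item on the worksheet, and an occasional wasted swab when a consented baby is not randomised. The sample size and the number of visits do not change.

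The change removes the influence of known allocation on how the baseline swab is taken. It does not guarantee a baseline result, because a sample can be lost or a culture can fail. Nor does it deal with replacement for missing post-baseline swabs, or with the day 3 and day 8 swabs, which are still collected with the allocation known.
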